3. RECRUITMENT PLAN

We plan to enroll approximately 200 subjects in total.

1. We will scan approximately 200 women who meet the entry requirements described below. This number may vary slightly because we will scan women with suspicious findings on mammography until we find 30 cancers, verified by the subsequent biopsy. Therefore it is not possible to report the exact number of women who will be in this group.
2. We will scan 150 healthy women with dense breasts and/or women who have risk of breast cancer that is average or higher.

Dense breasts are defined as categories C and D, defined in the American College of Radiology (ACR) BiRads manual. We will also follow ACR guidelines for risk categories. The ACR defines intermediate risk as those patients with a lifetime risk for breast cancer of 15%-20%. This includes women with a personal history of breast cancer, history of proven lobular neoplasia, atypical ductal hyperplasia or other women with 15%-20% risk based on risk models.

4. ELIGIBILITY.

Inclusion criteria:

- Women who have a mammographically and/or sonographically identified finding that will require image guided biopsy.
- OR
- For the ‘screening group’ we will recruit women between ages of 30 –70 who have above 10% lifetime risk of breast cancer or who have dense breasts (based on BIRADS score) but who currently do not have any diagnosis of breast cancer.
- We will select women for the screening group and the group of women with suspicious mammographic findings so that the two groups are well-matched. Our target is to match the percentage of parous and non-parous women, and premenopausal and post-menopausal women. In addition we will match the age distribution in the two groups.

Exclusion criteria:

- Women with a history of adverse reactions to contrast media.
- Women who are pregnant.
- Patients who are demonstrated to be at risk for an allergic reaction or nephrogenic systemic fibrosis (NSF) will be excluded from the study. Details as to how patients are evaluated for these risks are provided below (see ‘Potential Risks’).

5. STUDY DESIGN.

Enrollment:

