1. Approximately 50 women with suspicious findings on mammography who are scheduled for biopsy will be recruited. We expect this will result in 30 cancers and 20 benign lesions. **When possible**, we will perform MRI scans before the biopsy so that biopsy will not affect MRI results. Lesions will be classified as benign and malignant based on the subsequent biopsy. We will continue scanning until we have scanned 30 women with biopsy-confirmed malignancy. We estimate that

this will require a total of 50 scans, but the total number may turn out to be slightly higher or slightly lower.

2. We will also recruit 150 women with dense breasts and/or women who have intermediate risk of breast cancer for this study.

MRI scans:

Women will receive a mammogram and an MRI-screening exam. The MRI screening exam will consist of calibration scans, bilateral T2-weighted scans, and a DCEMRI scan. The duration of the entire protocol will be less than 15 minutes.

Ground truth assignment:

Assignment for the group who will have biopsy based on mammogram and/or ultrasound:

- a. **Surgical pathology will be the gold standard for these patients for the lesions previously identified on mammogram or ultrasound.**
- b. **Any additional lesions detected on MRI will follow the assignment as below for the screening group.**

Assignment for the dense breast/intermediate risk group:

- a. Women who have no cancer found on MRI will be classified as having no cancer.
- b. If additional lesions are deemed suspicious on MRI and these lesions are biopsied, they will be classified as benign or malignant based on biopsy surgical pathology results.
- c. If additional lesions are found on MRI but physicians elect not to biopsy based on the findings, these lesions will be assumed to be benign for the purposes of this study. In some cases, women may be referred for follow-up exams, e.g. in 6 months. In these cases, lesions that are still not biopsied after 6 month follow-up will be assumed to be benign for the purposes of this study.

Reader Study:

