Patients with scheduled biopsy will undergo the research MRI prior to their biopsy. At the time that the biopsy is recommended, the radiologist will identify the patient as one who will be having a biopsy and could qualify for research MRI. The breast care treatment teams (high risk clinic, surgery clinic) will contact the Radiology Research Coordinator if they have a patient that they believe could be eligible for the study. Once identified, the patient's name and MRN will be given to the research coordinator. She will be contacted by phone regarding the research study by the research coordinator. The

study will be explained to her, and she will be asked about her interest in participating. Questions, if any, will be answered. If interested, she will be scheduled in an MRI time slot. Biopsy patients will be scheduled for their MRI in the same visit unless they prefer otherwise. Prior to the MRI, they will be asked to read and sign the informed consent document by the research coordinator.

Data will be collected from the subjects regarding their race and ethnicity, age, weight, height, menopausal status, last menstrual cycle date.

All routine precautions will be taken prior to the MRI scans (screening for metallic or electronic (e.g., pace-maker) implants, removal of all metallic objects, etc.).

Patients with dense breasts and those referred for intermediate risk:

Women age 30-60 with dense breasts presenting for screening mammography are one of the target populations. The radiologist will identify scheduled mammography screening patients who are known to have mammographically dense breasts based on prior screening mammograms. Once identified, the patient's name and MRN will be given to the research coordinator. In cases identified by the Breast Center or Cancer Risk Clinic as intermediate risk, the research coordinator will be contacted about the patient.

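### MRI comes before biopsy only where feasible in Section 5 but always in Section 6, and no rule says how a post-biopsy scan is counted or analysed

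*Combined protocol and SAP*

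**What the plan says.** **Timing, conditional.** Section 5, Enrollment, item 1, opens its timing sentence with "When possible" (in bold) and continues: "we will perform MRI scans before the biopsy so that biopsy will not affect MRI results".

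**Timing, unconditional.** Section 6, on patients with lesions found by mammography or ultrasound: "Patients with scheduled biopsy will undergo the research MRI prior to their biopsy". The same section adds: "Biopsy patients will be scheduled for their MRI in the same visit unless they prefer otherwise". That sentence does not give the order of MRI and biopsy within the visit.

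**Wording that presumes MRI first.** Section 3 describes scanning "until we find 30 cancers, verified by the subsequent biopsy". Section 5 says: "Lesions will be classified as benign and malignant based on the subsequent biopsy".

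**Case count.** Section 5: "We will continue scanning until we have scanned 30 women with biopsy-confirmed malignancy". The timing of the scan is not mentioned. On yield: "We expect this will result in 30 cancers and 20 benign lesions".

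**Analysis.** Section 5, Statistical Power, names Ktrans and initial time of enhancement as primary endpoints, tests each AUC against 60%, and picks an optimal threshold for each parameter. It places some women with biopsy-proven benign lesions among the controls. It has no rule for scans taken after biopsy. The data items listed in Section 6 do not include a biopsy date or time.

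**Use of the results.** Section 2 draws the cutoffs from the biopsy group (item 2) and bases the false-positive rates on them (items 4 and 5).

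**The concern.** The two sections cannot both govern. One makes pre-biopsy scanning an aim with exceptions; the other makes it a fact. The difference matters because the plan gives its own reason for the order: biopsy can alter what the MRI shows. Having named the hazard, it leaves room for it and does not say how it would be handled.

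The exposure is unequal between the groups compared. Every case comes through the biopsy pathway. The 150 screening women have no biopsy scheduled before their scan; if they are biopsied at all, it is because of the MRI. The biopsied benign lesions share the cases' exposure but are a small part of the controls. A biopsy effect would therefore be partly confounded with cancer status, and matching on age, parity and menopausal status would not remove it.

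Both primary endpoints are enhancement measures read from these scans. An effect could inflate or mask the apparent discrimination, move the cutoffs, and so move the false-positive rates. If the handling is decided after the ROC curves are seen, the choice is open to the data.

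**Working it through.** **1. The plan's own figure.** Inputs from Section 5, Statistical Power: 30 cases, 170 controls, null AUC 0.60, detectable AUC 0.74, 5% level. Power and sidedness are not stated; I assume 80% power. The Hanley-McNeil variance for AUC = A with n₁ cases and n₀ controls is

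[A(1−A) + (n₁−1)(A/(2−A) − A²) + (n₀−1)(2A²/(1+A) − A²)] / (n₁n₀).

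This gives a standard error of 0.0585 at 0.60 and 0.0545 at 0.74. One-sided power at 0.74 is Φ((0.14 − 1.645 × 0.0585)/0.0545) = Φ(0.80) = 79%. The detectable AUC at 80% power is 0.742, which rounds to the stated 0.74. A two-sided 5% test gives 0.760, and 68% power at 0.74. The stated figure therefore reproduces as a one-sided test, and the timing issue does not show it to be wrong.

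**2. Illustration, cases only.** Assumptions, none of them from the documents: equal-variance normal scores, true AUC 0.74, a share f of case scans taken after biopsy, and a shift of c SD in those scans.

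- Separation: d = √2 × Φ⁻¹(0.74) = 0.91.
- AUC of a shifted scan: A(c) = Φ((d + c)/√2), so A(−0.5) = 0.614 and A(+0.5) = 0.841.
- Observed AUC = (1 − f) × 0.74 + f × A(c).
- At f = 0.10: 0.666 + 0.061 = 0.727, or 0.666 + 0.084 = 0.750.
- At f = 0.30: 0.518 + 0.184 = 0.702, or 0.518 + 0.252 = 0.770.

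**3. Illustration, with the benign lesions shifted too.** Suppose all 20 expected benign lesions are controls (170 = 150 + 20) and the same share of them shifts by the same amount. The affected share of controls is g = f × 20/170, which is 0.012 at f = 0.10 and 0.035 at f = 0.30. Then

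AUC = [(1−f)(1−g) + fg] × 0.74 + f(1−g) × A(c) + (1−f)g × A(−c).

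At f = 0.30 and c = −0.5: 0.686 × 0.74 + 0.289 × 0.614 + 0.025 × 0.841 = 0.706.

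| Share f | Shift c | AUC, cases only | AUC, benign lesions shifted too |
|---|---|---|---|
| 10% | −0.5 SD | 0.727 | 0.729 |
| 10% | +0.5 SD | 0.750 | 0.749 |
| 30% | −0.5 SD | 0.702 | 0.706 |
| 30% | +0.5 SD | 0.770 | 0.766 |

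Section 5 also gives a control count of 60 to 70. With 65 controls, g = 0.30 × 20/65 = 0.092, and the last two rows become 0.712 and 0.759.

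**4. Effect on the test.** Using the step 1 formula with 30 and 170, one-sided power of 79% at 0.74 becomes 72% at 0.729 and 57% at 0.706.

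**The case against.** The strongest reply is that the plan's default is clear. Women are recruited when a biopsy is scheduled, two sections speak of the subsequent biopsy, and Section 6 puts the MRI first. On that reading the qualifier in Section 5 is only a feasibility allowance, and post-biopsy scans would be exceptions. This stands, and it makes the larger shares in the illustration hard to support. It does not remove the gap, because an allowance for exceptions needs a rule for them. With 30 cases, each exception is 1/30 = 3.3% of the case set.

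A reader might infer more than the documents support:

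- **That the plan counts post-biopsy scans toward the 30 cancers.** No sentence says so. The count is silent on timing, so the question is open.
- **That the effect falls on one side only.** It does not. The roughly 20 biopsied benign lesions face the same risk, which offsets part of the bias, as step 3 shows.
- **That the AUCs will be materially biased.** Share, size and direction are all unknown. At 10% and 0.5 SD the change is about 0.01, against a 95% half-width of 1.96 × 0.0545 = 0.107. Bias does not average out as sampling error does, but nothing shows that it would be large.
- **That distorted cutoffs would pass unchecked into later work.** Section 5 calls this a pilot and plans validation in a larger cohort. The direct consequence is for the estimates and false-positive rates of this study.

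**Conclusion.** The inconsistency between Sections 5 and 6 is real, and the missing analysis rule matters because the plan itself says that biopsy can affect the MRI. Any post-biopsy scans would enter mainly the case set, to a lesser extent the biopsied benign controls, and not the 150 screening women. They could bias the two primary AUCs, the cutoffs and the false-positive rates, in either direction.

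The size cannot be established from the documents. The movements of about 0.01 (10% of scans) and about 0.03 to 0.04 (30%) rest on an assumed true AUC of 0.74, an assumed 0.5 SD shift and a normal model; they show scale and do not predict. No stated figure in the plan is shown to be wrong. This is an inexpensive improvement that should be made before the data are analysed, not a defect that undermines the study.

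**What to change.** 1. Reconcile Section 5 (Enrollment, item 1) with Section 6, so that the plan makes one statement on the order of MRI and biopsy. Which order applies is for the investigators to settle.
2. Record the biopsy date and time relative to the MRI for every woman in the biopsy group, benign as well as malignant.
3. Prespecify that the AUCs and cutoffs are estimated from scans acquired before biopsy, and report all scans as a sensitivity analysis.
4. State whether the target of 30 cancers means 30 with a pre-biopsy scan.

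**Cost.** One data field, a few sentences and one extra analysis. If exceptions occur, the primary set has fewer cases and wider intervals. By the formula in step 1 at AUC 0.74 with 170 controls, losing 3 of 30 cases raises the standard error from 0.0545 to 0.0573, and the 95% half-width from 0.107 to 0.112. If the 30 must all be pre-biopsy, accrual runs slightly longer instead. Keeping all cases in the primary analysis, with pre-biopsy scans as the sensitivity analysis, would be a defensible alternative if fixed in advance. The order proposed here follows the plan's own reason for scanning first. If no exceptions occur, nothing is lost.

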Thirty women with biopsy-confirmed breast cancer and between sixty and seventy controls (women with dense breasts and/or moderate breast cancer risk, frequency-matched by parity, age, and menopausal status; control group also includes some women with biopsy-proven benign lesions) will be scanned using the short MRI protocol. Receiver Operating Characteristic (ROC) curves and statistics will be constructed for several MRI parameters of interest: Ktrans, initial time of enhancement in parenchyma and suspicious lesions, new approaches to calculating Ktrans and the arterial input function based on early enhancement, and number and size of arteries feeding suspicious lesions and rate of enhancement of those blood vessels. The primary endpoints of this study are Ktrans and 'initial time of enhancement'. Optimal diagnostic thresholds will be determined for each parameter, where the optimal threshold for a given parameter is defined as the parameter value which has highest sum of specificity and sensitivity over all possible thresholds with specificity > 80%. We will also test whether the area under the curve (AUC) for each parameter exceeds 60%. 95% confidence intervals will be constructed for the AUC for each curve and the sensitivity and specificity of each optimal threshold. For our two primary endpoints (Ktrans and initial time of enhancement), our sample of 200 subjects (30 cases + 170 controls) is large enough to detect AUCs of 74% (i.e., a difference of 14%) at the 5% significance level.

Thresholds determined in this pilot study will later be validated in a larger cohort – this is the subject of an RO1 proposal to be submitted soon. In the future cohort, we will construct covariate-adjusted ROC curves that will be used to calculate thresholds, specificities, and sensitivities for patients with different breast cancer risk factors (Gail scores, family history, etc.).

We will also produce ROC curves for each reader in the 'reader study' to obtain a preliminary estimate of how standard evaluation of abbreviated MRI datasets compare with the quantitative analysis described above. However, this is an exploratory aim of the study and the study is not powered to evaluate the statistical confidence of these measurements.

6. PROCEDURES TO WHICH HUMANS WILL BE SUBJECTED:

Patients with lesions detected on mammography or ultrasound:

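### Unbiopsied extra MRI lesions can be scored benign without verification, on a decision that rests partly on enhancement, and the ROC unit that determines the effect is not stated

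*Combined protocol and SAP*

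**What the plan says.** Section 5, Ground truth assignment, has two lists.

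For the biopsy group, rule (a) states: "Surgical pathology will be the gold standard for these patients for the lesions previously identified on mammogram or ultrasound". Rule (b) adds: "Any additional lesions detected on MRI will follow the assignment as below for the screening group".

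For the screening group, rule (b) has suspicious lesions that are biopsied "classified as benign or malignant based on biopsy surgical pathology results", with no time limit. Rule (c) states: "If additional lesions are found on MRI but physicians elect not to biopsy based on the findings, these lesions will be assumed to be benign". On women referred to follow-up it adds: "lesions that are still not biopsied after 6 month follow-up will be assumed to be benign for the purposes of this study".

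No rule uses imaging stability, no category exists for a lesion of unknown status, and no sensitivity analysis of the labels is planned.

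Section 2, item 6, bases suspicion on the attending radiologist's reading of the MRI, with BI-RADS 0, 4 and 5 as the suspicious codes. Items 4 and 5 make the false-positive rate an aim. Section 5, Statistical Power, names Ktrans and initial time of enhancement as primary endpoints and tests each AUC against 60%. Its power sentence uses "our sample of 200 subjects (30 cases + 170 controls", while the same paragraph opens with "between sixty and seventy controls". On the biopsy group, Section 5, Enrollment, says: "We expect this will result in 30 cancers and 20 benign lesions".

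**The concern.** Rule (c) makes absence of biopsy the criterion for benign. Stability, resolution and pathology play no part. As written, a followed lesion that grew but was not biopsied is benign.

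Two consequences follow. First, the attending's reading, which includes enhancement, influences which lesions are biopsied, and so which get a verified label. The primary endpoints are themselves measures of enhancement, so test and reference standard are partly tied together. Second, a suspicious lesion that reaches the benign label this way is a false positive by assumption, in a study that sets out to estimate the false-positive rate.

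The direction of bias is not fixed. Hidden cancers that enhance like the cases count as false positives and lower the AUC and specificity. Hidden cancers that enhance slowly count as true negatives, and apparent sensitivity is too high. The cutoffs from this pilot are to be carried into a larger cohort.

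**Working it through.** **1. What the rules assign to an extra MRI lesion**

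- Biopsied: pathology decides (screening rule (b)).
- Not biopsied because the findings did not call for it: benign (rule (c), first sentence).
- Followed and unbiopsied at 6 months: benign, whatever the follow-up showed (rule (c), last sentence).
- Removed together with an index cancer: no clear rule. Biopsy-group rule (a) covers only lesions already seen on mammogram or ultrasound, and the condition in rule (c)'s first sentence is not met on its face.
- Suspicious, but biopsy declined and no follow-up made: no clear rule. Section 8 leaves further work-up to the woman's choice, at her own or her insurer's cost, so this can happen.

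**2. The plan's own figure**

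Inputs from Statistical Power: 30 cases, 170 controls, null AUC 0.60, alternative 0.74, 5% level. Sidedness and power are not stated; one-sided testing is assumed. The Hanley-McNeil variance is [A(1−A) + (n1−1)(Q1−A²) + (n0−1)(Q2−A²)]/(n1·n0), with Q1 = A/(2−A) and Q2 = 2A²/(1+A).

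- A = 0.60: (0.24 + 29×0.0686 + 169×0.0900)/5100 = 0.00342, SE 0.0585.
- A = 0.74: (0.1924 + 29×0.0397 + 169×0.0818)/5100 = 0.00297, SE 0.0545.
- Power = Φ[(0.14 − 1.645×0.0585)/0.0545] = Φ(0.80) = 78.9%.

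With the Obuchowski variance the power is 81.1%. The 74% figure therefore reproduces with one-sided testing and about 80% power. Two-sided testing gives 67.9% or 71.2%.

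**3. Dilution by hidden cancers**

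Take n true negatives and add m cancers labelled benign that score like the cases. Against the cases such a lesion has an AUC of 0.5, so observed AUC = (n×AUC + m×0.5)/(n + m). The true AUC of 0.80 and m = 3 or 5 are assumptions.

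| True negatives | m = 3 | m = 5 |
|---|---|---|
| 170 (power sentence) | 137.5/173 = 0.795 | 138.5/175 = 0.791 |
| 65 (middle of 60–70) | 53.5/68 = 0.787 | 54.5/70 = 0.779 |
| 20 (benign biopsy-group lesions) | 17.5/23 = 0.761 | 18.5/25 = 0.740 |

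The first two rows are a by-woman ROC, where hidden cancers can come only from control women. The last row is a by-lesion analysis in the biopsy group.

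**4. Effect on power, by woman**

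Start from the plan's 0.74 and count the hidden cancers within the 170 controls, so that observed AUC = 0.74 − 0.24×m/170. With one-sided 5% and Hanley-McNeil:

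- m = 3: AUC 0.736, power 76.5%.
- m = 5: AUC 0.733, power 74.8%.
- m = 17 (10% of controls): AUC 0.716, power 63.9%.

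**5. Effect on the cutoff, by lesion**

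The threshold must keep specificity above 80%. With 20 benign lesions, 3 may lie above it (17/20 = 85%; 16/20 = 80% fails). With 3 hidden cancers added, 4 of 23 may (19/23 = 82.6%; 18/23 = 78.3% fails). If all 3 hidden cancers lie above the cutoff, only 1 truly benign lesion may join them, so the cutoff is pushed up.

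**6. The opposite direction**

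Suppose 27 of 30 recognised cancers lie above the cutoff: 90% sensitivity. If 3 or 5 hidden cancers all lie below it, the true value is 27/33 = 82% or 27/35 = 77%. Both the counts and their position are assumed.

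**The case against.** The strongest reply has four parts.

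- **Scope of rule (c).** A reader might infer that every unbiopsied extra lesion is declared benign, including a second cancer found in the surgical specimen. The text does not say so. The first sentence of rule (c) is limited to a decision made on the findings. Nothing says that it overrides a malignant specimen, and the plan uses the term surgical pathology for biopsy material too. Nor is a lesion biopsied after the 6-month visit clearly fixed as benign, since rule (b) has no time limit. This stands: these cases are gaps, not explicit benign labels.
- **Unit of analysis.** Statistical Power counts women. A woman with proven cancer is a case, so her second lesion adds no negative. This stands for a by-woman ROC. It does not settle the matter, because Section 2, item 2, sets cutoffs for benign and malignant lesions, and biopsy-group rule (b) has little purpose if extra lesions are never analysed.
- **Indirect dependence.** The label comes from the attending's interpretation, not from a Ktrans or timing cutoff. This is correct, and the dependence is partial. It is not absent, because non-mass enhancement is among the findings that define suspicion.
- **Pilot status.** The thresholds will be validated later. That limits the harm, but it does not tell the later study how far its starting cutoffs rest on unverified labels.

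**Conclusion.** The point holds as a verification gap. The plan can count unverified cancers as benign, by a decision that is not independent of the primary endpoints, and it has no means of showing how much this matters.

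The size depends on the unit. In a by-woman ROC with 170 negatives, 3 or 5 hidden cancers that score like the cases cost 0.005 to 0.009 of AUC, which is small. Against about 20 benign lesions, the same counts cost 0.04 to 0.06. These losses are near the upper end for the assumed counts, since lesions judged not to need biopsy may score lower than the cases. In that event the AUC is diluted less, and the risk shifts to overstated sensitivity.

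All counts are assumptions, because the documents give neither the number of unbiopsied extra lesions nor their malignancy rate. It would go too far to conclude that true cancers will enter the ROC as benign, or that the AUC test as powered is seriously compromised. The documents support only that mislabelling can occur. This is an inexpensive improvement that should be made; it does not invalidate the design.

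**What to change.** 1. State whether the ROC unit is the woman or the lesion, for the AUC test and for the cutoffs. Reconcile the two control counts in Statistical Power at the same time.
2. Let any pathology obtained before database lock, from core biopsy or surgical specimen and whenever taken, set the label of every lesion it covers, extra MRI lesions included.
3. Flag as unverified every suspicious lesion (BI-RADS 0, 4 or 5) that has neither pathology nor a benign work-up. Flag also every followed lesion without documented stability or resolution, including those with missed follow-up.
4. Report the AUC, cutoffs, sensitivity, specificity and false-positive rate three ways: unverified lesions excluded, all benign, and all malignant. Exclusion alone is not enough, because the lesions left out are not a random subset.

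The change affects analysis labels only and requires no biopsy, scan or visit. The cost is protocol wording, the work of matching MRI lesions to pathology reports, and slightly wider intervals where lesions are excluded. Lesions never called suspicious and not sent for follow-up remain assumed benign, so the dependence on the attending's reading is reduced but not removed. The report should state that as a limitation.

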The T2-weighted scans and high resolution post contrast T1-weighted scans will be evaluated by Radiologists using conventional diagnostic procedures. Radiologists will also evaluate ultrafast scans to identify regions with anomalously rapid enhancement, or abnormally enhancing blood vessels in ultrafast images. Based on this evaluation they will assign a probability of malignancy, on a scale from 1 – 10. Three independent readers will evaluate images and assign a probability of malignancy. We will calculate ROC curves for each of the 3 readers to assess 1) variability of Reader's 'probability of malignancy' scores 2) AUCs for Radiologists compared to the quantitative parameters described above. The Reader study is an exploratory aim and the study is not powered to perform this analysis with reasonable statistical confidence. The goal is simply to obtain

a preliminary assessment that can provide a basis for future studies with a larger number of patients and readers.

Statistical Power:

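### The reader study names variability of the readers' malignancy scores as a goal, but its only tool, one ROC curve per reader, cannot measure it

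*Combined protocol and SAP*

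**What the plan says.** Section 5, Reader Study, sets up the reading: "Three independent readers will evaluate images and assign a probability of malignancy". Of the radiologists it says that "they will assign a probability of malignancy, on a scale from 1 – 10".

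The analysis has two goals. The first is stated together with its method: "We will calculate ROC curves for each of the 3 readers to assess 1) variability" of the readers' probability-of-malignancy scores. The second is "AUCs for Radiologists compared to the quantitative parameters described above". The target of the first goal is therefore the scores themselves, not the readers' accuracy.

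Section 5, Statistical Power, returns to the readers once: "We will also produce ROC curves for each reader in the 'reader study' to obtain a preliminary estimate" of how standard evaluation compares with the quantitative analysis. That sentence serves the second goal only.

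The documents name no kappa, intraclass correlation, within-woman standard deviation, pairwise difference or multi-reader model. The one reproducibility item, in Section 2 (10 volunteers), concerns the MRI protocol and not the readers.

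The status of the aim is plain: "The Reader study is an exploratory aim and the study is not powered to perform this analysis with reasonable statistical confidence".

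**The concern.** A ROC curve is built from one reader's scores and the true disease status. It depends only on how that reader ranks cancers against non-cancers. Two consequences bear on the first goal.

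- **No pairing between readers.** If one reader's scores are rearranged among the cancers, or among the non-cancers, the curve is unchanged. Two readers with the same curve may agree fully or poorly on individual women.
- **No sensitivity to scale.** If one reader gives every woman a higher score, the curve and AUC stay the same, but the false-positive rate at a given score does not.

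Followed literally, the plan yields three curves and no estimate of score variability. The likely misreading is that three similar AUCs mean the readers agree. This matters somewhat more than usual here, because Section 2 gives the evaluation of false-positive rate as the purpose of the reader study, and a scale difference between readers changes exactly that rate.

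**Working it through.** The documents give no sample size, power or agreement figure for the reader study, so there is nothing of the plan's own to reproduce. The check is by construction.

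**Inputs**
- Three readers, scores 1 to 10 (Section 5, Reader Study).
- 30 cases and 170 controls (Section 5, Statistical Power: "our sample of 200 subjects (30 cases + 170 controls"). The same section also mentions sixty to seventy controls; the invariance does not depend on the count.
- Score distribution: not given. Assumption: normal scores with SD 2, rounded and limited to 1-10, tried at two levels of accuracy (AUC about 0.77 and about 0.89).

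**Step 1. Invariance.** At cut t, sensitivity is the share of cases with score ≥ t, and the false-positive rate is the share of controls with score ≥ t. Both are proportions within a class, so rearranging scores within that class leaves them unchanged. Adding a constant c to every score gives at t + c the pair formerly found at t, so the set of points, and hence the curve, is the same.

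**Step 2. Identical curves, different agreement.** In each row the three readers' empirical curves were identical at every point. Agreement is the exact score match between pairs of readers. The ICC is two-way random-effects, absolute agreement.

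| Construction | AUC (all three) | Exact pairwise agreement | ICC |
|---|---|---|---|
| Identical readers | 0.773 / 0.892 | 100% / 100% | 1.00 / 1.00 |
| Scores permuted at random within class | 0.773 / 0.892 | 19-22% / 12.5-21.5% | 0.15 / 0.27 |
| Scores shifted cyclically within class | 0.773 / 0.892 | 0% / 0% | -0.13 / 0.11 |
| Constant offset of +1 and +2 points | 0.774 / 0.885 | 0% / 0% | 0.77 / 0.83 |

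(Base scores were capped at 8 in the last row to leave room for the offset, hence the slightly different AUC.) The curves cannot tell the rows apart; a statistic on the paired scores can.

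**Step 3. A less extreme case.** Assume bivariate normal scores and two readers of equal accuracy, each with 90% specificity (an assumption). Let ρ be their correlation among non-cancers. The chance that the second reader also flags a false positive of the first is P(both flag)/0.10:
- ρ = 0: 0.0100/0.10 = 10%
- ρ = 0.5: 0.0324/0.10 = 32%
- ρ = 0.9: 0.0689/0.10 = 69%

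The readers' expected AUCs do not depend on ρ. Agreement on flag versus no flag among non-cancers is 1 - 2 × (0.10 - P(both flag)), that is 82%, 86% and 94%.

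**Step 4. Scale shift.** For normal scores in non-cancers and a cut 1 SD above the mean, the false-positive rate is 1 - Φ(1) = 0.159. For a reader who scores 1 SD higher throughout, it is 1 - Φ(0) = 0.50. Curve and AUC are the same for both.

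**Step 5. Pairing in the second goal.** Readers and MRI parameters are evaluated in the same women. In a simulation with 30 + 170 women and two measures each of true AUC 0.85 (assumed), the standard error of the AUC difference was about 0.053, 0.040 and 0.019 at correlation 0, 0.5 and 0.9. Treating correlated AUCs as independent would overstate the uncertainty.

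**The case against.** The strongest reply is that the aim is declared exploratory and unpowered, that the primary endpoints are Ktrans and initial time of enhancement, and that all three readers' scores are collected anyway, so agreement can be computed later with nothing lost. All of this is true and keeps the point small. It does not remove it: the fault is a mismatch of method and target, which more patients would not cure.

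A second reply is that the curves are not empty. They show variation in accuracy between readers, and curves that differ by more than chance imply that the scores differ. An empirical curve on a 1-10 scale is also computed from sensitivity and false-positive rate at each cut, so a scale shift would be visible in those tabulated values, though not in the curve's shape or AUC. This stands. What fails is the inference in the other direction, from similar curves to agreement.

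Three stronger readings are tempting, and the documents do not support them.

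- *The readers will disagree on nearly every woman.* Complete disagreement arises only in artificial arrangements and by exact score match. With the constant offset the ICC is still 0.77-0.83, and in Step 3 the readers agree on 82-94% of non-cancers. If 80% of controls share one score, rearrangement can make at most 20% + 20% = 40% of controls differ between two readers.
- *The plan ignores pairing when it compares AUCs.* The text says only that reader AUCs will be compared with the parameters. It specifies no interval or test for readers and excludes no paired method.
- *A figure needed to size a later study is lost.* The Reader Study paragraph speaks only of a preliminary assessment as a basis for larger studies; it names no sizing figure. Variation in AUC between readers may itself be useful for planning.

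**Conclusion.** The point holds and is minor. The Reader Study paragraph names variability of the 1-10 scores as its first goal and gives per-reader ROC curves as the only tool. Those curves cannot measure it. This follows from how a ROC curve is defined and rests on no assumption about the data.

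The sizes are illustrations under assumptions that the documents do not supply: identical curves with an ICC anywhere from -0.13 to 1.00 at AUC 0.77 (0.11 to 1.00 at AUC 0.89), and a false-positive rate of 50% against 16% for a 1 SD shift under normal scores. They show what the curves can hide, not what these three readers are expected to do. The remark on pairing in the second goal is a recommendation, not an error in the text. No primary endpoint is affected.

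**What to change.** In Section 5, Reader Study, separate the two goals.

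1. **Score variability.** Analyse the three readers' scores woman by woman. Report a two-way random-effects intraclass correlation for absolute agreement (or a weighted kappa), with a 95% interval from a bootstrap over women. Report each reader's sensitivity and false-positive rate at a common score.
2. **Comparison with the MRI parameters.** Keep the per-reader ROC curves and AUCs. If an interval is given for an AUC difference, use a paired method on the same women (DeLong, or a bootstrap over women).

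If a reader-averaged AUC is reported with an interval that resamples women only, say that the interval is conditional on these three readers. It does not cover the variation expected with other readers.

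The cost is a few sentences and minor analysis of scores already planned. No extra readers, reads or patients are needed, and the aim stays exploratory.
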